## 10 Study Procedures

#### 10.1 Patient selection

Patients who are over 50 years of age taking 3 or more medicines will be identified through searches of practice disease registers. Other ways of identifying these patients will be at the time of medication reviews and engagement with primary care practitioners in General Practice across the two sites who will be informed about the study and its purpose. We will focus initially on patients on medication for cardiovascular disease, mental health, pain and gastroprotection.

#### 10.2 Questionnaire

Information on patients adverse reactions will be gathered in the form of review of patient records by their GP and questionnaires at multiple timepoints throughout the study; pre-PGx report, 1 month, 3 month, 6 month and 12 month post-medication review (see appendix 1). This will include capture of data on number of GP visits, medication use, hospital admissions, adverse drug reactions

#### 10.3 Sample processing

Samples relating to the study will be assigned a unique study identifier. A saliva sample will be sent to a GCP lab for germline DNA extraction. DNA will be processed using the Illumina Global Diversity Array. Raw data will be transferred to Congenica Ltd (UK) via secure sftp. Raw genetic data will be processed by Congenica into genotype data. Genotype data will be processed to a pharmacogenomic report (PGx) by Abomix (Finland) and returned to Congenica Ltd and subsequently the patients GP (see appendix 2). Participant samples will be held, managed, and disposed of in compliance to HTA regulations. DNA which has not been consented for further research will be destroyed at the end of the study. DNA which has been consented for further research will be destroyed no more than 10 years after the end of the study.

#### 10.4 Data collection

Information from the questionnaire will be collected at the designated timepoints and captured in a customized OpenApp study registry.

#### 10. 5 Management review

Phamacogenetic data from the patient will be used to suggest changes to prescribing within the confines of the authorization, based on guidelines from CPIC, DPWG and FDA and in the context of the patient history. The clinical decision for prescribing for each patient is however the physician's responsibility.

## 11 Patient journey and study flow chart

Please refer to Appendix 2/3.

## 12 Safety Events

This study uses medications with a marketing authorization in the UK, prescribed in accordance with the terms of that authorization and FDA labelling. Pharmacogenetic data from the patient will be used to suggest changes to prescribing within the confines of the authorization, NHS prescribing practices and NHS medication availability, based on guidelines from CPIC and DWPG, and in the context of the patient history. The clinical decision for prescribing for each patient is however the physicians responsibility.

#### a. Definitions

**Adverse Event (AE)**—any untoward medical occurrence in a participant whether it is considered to be related to the procedure or not, that includes a clinical sign, symptom, or condition and/or an observation of a near incident. This does not include pre-existing conditions recorded as such at baseline; continuous persistent disease or a symptom present at baseline that worsens following the procedure.

**Serious Adverse Event (SAE)** - any Adverse Event or untoward medical occurrence in a study participant that can be wholly or partly due to the procedure which resulted in any of the following:

- Death
- Is life-threatening (places the participant, in the view of the Investigator, at immediate risk of death)
- Requires hospitalisation or prolongation of existing hospitalisation (hospitalisation is defined as an inpatient admission, regardless of length of stay, even if it is a precautionary measure for observation, including hospitalisation for an elective procedure for a preexisting condition)
- Results in persistent or significant disability or incapacity (substantial disruption of one's ability to conduct normal life functions)
- Consists of a congenital anomaly or birth defect (in offspring of participants regardless of time of diagnosis)
- Is another important medical condition

Important medical events that may not be immediately life-threatening or result in death or hospitalisation but may jeopardise the participant or require intervention to prevent one of the outcomes listed in the definition of serious AE will also be considered serious.

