### b. Recording Adverse Events (AEs)

All Adverse Events will be recorded in the general practice notes in the first instance.

A record of all AEs, whether related or unrelated to the treatment, will also be kept in the CRF and the Sponsor's AE Log.

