#### 15.1.2 Secondary endpoints

# and type of adverse effects reported by patients pre and post receipt of PGx data # Actionable PGx variants which do not impact on current medication Anxiety measures at baseline, 1 mth, 3 mths, 6 mths and 1 year after consent Patient acceptance of the use of PGx

The time taken to process and receive DNA/PGx results from the time of consent to the project. Fraility index measures at baseline, 1 mth, 3 mths, 6 mths and 1 year after consent Service use review (eg. #hospital admissions, GP appointments and recorded adverse effects at baseline and 1 year)

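### Read literally, the adverse event definition excludes worsening of a baseline disease or symptom, so non-serious worsening after a PGx-prompted prescribing change need not reach the CRF or AE Log

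*Protocol*

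**What the plan says.** Protocol section 12a defines an adverse event as "any untoward medical occurrence in a participant whether it is considered to be related to the procedure or not". The next sentence sets the exclusions. It begins "This does not include pre-existing conditions recorded as such at baseline" and, after a semicolon, continues with "continuous persistent disease or a symptom present at baseline that worsens following the procedure".

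The same section defines an SAE as "any Adverse Event or untoward medical occurrence in a study participant that can be wholly or partly due to the procedure" that meets a seriousness criterion. The hospitalisation criterion covers any inpatient admission, "including hospitalisation for an elective procedure for a preexisting condition".

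On recording, section 12b says that events go first into the general practice notes, and then: "A record of all AEs, whether related or unrelated to the treatment, will also be kept in the CRF" and the Sponsor's AE Log. Section 12c has that log sent to the Sponsor on request and every 3 months.

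Adverse effects are also collected elsewhere. Section 10.2 gathers adverse reactions, GP visits, medication use and hospital admissions by GP record review and questionnaire, before the PGx report and at 1, 3, 6 and 12 months after the medication review. Section 15.1.2 lists among the secondary endpoints the number "and type of adverse effects reported by patients pre and post receipt of PGx data", and a service-use review at baseline and 1 year.

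**The concern.** Under section 7.1, participants take three or more medicines for cardiovascular health, musculoskeletal pain, gastro protection and mental health. Sections 10.5 and 12 say that the PGx data will be used to suggest changes to prescribing. If a change does not suit a participant, one plausible sign is that a condition already present gets worse. The exclusion sentence takes that kind of event out of the adverse event definition.

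The AE Log is the only periodic safety report to the Sponsor that the protocol describes. If non-serious worsening need not enter it, the log will show new complaints but not deterioration of old ones, and that gap favours an appearance of no harm. It also matters for the later study that this one is meant to inform (section 15b), because the AE experience carried forward would be incomplete in the same way.

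**Working it through.** No arithmetic applies. The protocol states no rate of adverse events, adverse reactions or worsening, so the check is a reading of the sections against each other.

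**Step 1: what the exclusion covers.** Both items joined by the semicolon are governed by the opening phrase of the sentence, which says what an adverse event does not include. No second verb turns the later item into an inclusion. It is slightly unclear whether the clause about worsening attaches to the symptom only or to the disease as well. On either reading a baseline symptom that worsens is excluded, and a persistent disease is excluded without any exception for deterioration. Nothing else in section 12 brings it back.

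**Step 2: what follows for recording.** Section 12b's duty to record in the CRF and AE Log applies to adverse events. An occurrence outside the definition carries no such duty. Non-serious worsening may still appear in the GP notes as ordinary care, but the protocol does not require it to be carried into the study's safety record.

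**Step 3: the SAE route.** The SAE definition has two entry terms joined by 'or': an adverse event, or an untoward medical occurrence. Worsening that is not an adverse event can therefore still be an SAE if it is serious and at least partly due to the procedure. That condition depends on a term that section 12 does not define:

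| Section | Reference term |
|---|---|
| 12a | the procedure |
| 12b | the treatment |
| 12d | the study procedures |

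Section 9.3 describes consent to the study as consent to a saliva sample. If 'procedure' means sampling, serious worsening after a prescribing change does not clearly qualify. If it includes the PGx-informed review and its consequences, it does. The text does not settle which.

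**Step 4: consistency within 12a.** The adverse event definition leaves out pre-existing conditions and their worsening, while the SAE hospitalisation criterion expressly takes in an elective admission for a pre-existing condition. Because of the second SAE entry term this is not a formal contradiction. It does mean that a planned admission meets a seriousness criterion while a real but non-serious deterioration need not be logged.

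**Step 5: the other routes.** Section 10.2's questionnaires and record review, and section 15.1.2's endpoints, are not tied to the 12a definition and may capture worsening. Sections 10.4 and 13b put the questionnaire data in the study registry. No section sends them on to the AE Log or into safety reporting.

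**The case against.** The best defence has four parts.

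*The sentence may be a drafting slip.* The semicolon could mark a point where an inclusion was intended. That is possible, but then the sentence states the opposite of what was meant and still has to be corrected. Sites will work from the text as it stands.

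*Worsening is collected by other means.* This largely stands. A reader might infer that the study's safety data as a whole will miss worsening, and the documents do not support that. GP record review, repeated questionnaires, admissions and GP appointments all lie outside the 12a definition. The questionnaire (Appendix 1) and the Sponsor's safety reporting procedure cited in 12c are not shown, and neither can be assumed to repeat the exclusion. What remains is the gap in AE recording.

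*Serious worsening is not lost.* This also stands in part. A reader might infer that an SAE must first be an adverse event, so that the exclusion carries through to serious events. The second entry term in the SAE definition rules that out. What remains is the dependence on an undefined 'procedure'.

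*The pre/post endpoint is not shown to be affected.* A reader might infer that the exclusion would produce an artificial fall in adverse effects after the PGx report, with baseline complaints counted before but not after. Nothing applies the 12a definition to that endpoint: section 15.1.2 speaks of adverse effects reported by patients, and section 10.2 of adverse reactions. If 12a were applied consistently, the same sentence would also exclude conditions recorded at baseline from the earlier count, so the supposed fall would not follow.

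Finally, this is a non-randomised feasibility study without a safety primary endpoint. That limits the consequences but does not justify the wording.

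**Conclusion.** The point holds in a limited form. As written, section 12a excludes worsening of a disease or symptom present at baseline. Non-serious worsening after a PGx-prompted prescribing change therefore need not enter the CRF or the Sponsor's AE Log. Serious worsening can qualify as an SAE, subject to what 'procedure' means. Other data collection may capture some worsening but is not linked to the AE Log.

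The size cannot be given in events. Eligibility means that all participants enter on treatment in these clinical areas, but that says who could be affected, not how many will worsen. New reactions that were absent at baseline remain adverse events for everyone. Nor does the protocol rank harms: that worsening would be the main foreseeable one is an inference a reader might draw, not something the documents establish. The conclusion rests on the grammatical reading of one sentence and on the absence of any other provision in section 12 that restores worsening.

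**What to change.** 1. Amend section 12a so that a pre-existing condition that is unchanged from baseline is not an adverse event, but any worsening in severity or frequency after baseline is.
2. Define 'procedure' in section 12a so that it includes return of the PGx report and any prescribing change made at the PGx-informed review.
3. Use that one term in 12a, 12b and 12d in place of the present three.

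The CRF instructions should carry the same wording. The cost is a protocol and CRF text change and somewhat more AE entries, from practice records that section 10.2 already has GPs reviewing. The change is best made before data collection, because events that were not logged at the time are hard to recover reliably afterwards.

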### b. Recording Adverse Events (AEs)

All Adverse Events will be recorded in the general practice notes in the first instance.

A record of all AEs, whether related or unrelated to the treatment, will also be kept in the CRF and the Sponsor's AE Log.

#### c. Investigator Responsibilities relating to Safety Reporting

Collection, recording and reporting of AEs (including serious and non-serious events and reactions) to the Sponsor will be done according to the Sponsor's Safety reporting for non-CTIMP studies.

All SAEs will be recorded in the GP notes and the CRF, and the Sponsor's AE Recording Log. The AE Log will be sent to the Sponsor on request and every 3 months.

All SAEs will be reported both to the Sponsor & REC using the SAE report form for research other than CTIMPs (non-CTIMPs) published on the HRA website.

The Chief or Principal Investigator, or a member of the research team, at any participating site will complete the SAE form which will be e-mailed to [contact] within 48hrs of the Investigator becoming aware of the event, and via email to the relevant REC.

The Chief or Principal Investigator will respond to any SAE queries raised by the Sponsor as soon as possible. Follow-up reports must continually be completed within an acceptable time-frame and sent as detailed above until the reportable event is considered resolved.

Events will be followed up until resolution; any appropriate follow-up information will be clearly marked as such and reported to the sponsor as above in a timely manner.

Full reports should be completed and submitted to REC within 15 days of the event.

#### d. Notification of deaths

Only deaths that are assessed to be caused by the study procedures will be reported to the Sponsor. This report will be immediate.

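### Section 12d limits death reports to deaths assessed as caused by study procedures, contradicting the safety-reporting rules in sections 12a to 12c

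*Protocol*

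**What the plan says.** Four parts of section 12 of the protocol bear on a death.

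- **12a, Definitions.** An adverse event (AE) is "any untoward medical occurrence in a participant whether it is considered to be related to the procedure or not". Pre-existing conditions, persistent disease and baseline symptoms that worsen are then carved out. An SAE is narrower: an event "that can be wholly or partly due to the procedure which resulted in any of the following", and death is the first outcome listed.
- **12b, Recording.** "A record of all AEs, whether related or unrelated to the treatment" is to be kept in the CRF and the sponsor's AE log, as well as in the general practice notes.
- **12c, Investigator responsibilities.** "All SAEs will be reported both to the Sponsor & REC using the SAE report form". The form is e-mailed "within 48hrs of the Investigator becoming aware of the event", and full reports go to the REC within 15 days of the event. The AE log goes to the sponsor on request and every 3 months.
- **12d, Notification of deaths.** "Only deaths that are assessed to be caused by the study procedures will be reported to the Sponsor". Then: "This report will be immediate".

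**The concern.** Section 12d is the only passage written specifically for deaths, so a site with a death to handle is likely to turn to it first. Its test, that the death be assessed as caused by study procedures, is stricter than the 12a test, under which a possible or partial contribution is enough. A site cannot follow both.

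The study prompts medication changes in people over 50 who take three or more medicines. A death to which such a change may have contributed is the kind of event on which the sponsor most needs prompt notice. If 12d is followed, that notice is not given. With two participating practices, each could follow a different passage and report different deaths.

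**Working it through.** No arithmetic applies. The protocol states no death rate or expected event count, so the check is to take each kind of death through the four passages.

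| Death | Under 12a to 12c | Under 12d | Result |
|---|---|---|---|
| Assessed as caused by the procedure | SAE; to sponsor and REC, form within 48 hours | To sponsor, immediately | Reported either way; timing differs |
| Possibly or partly due to the procedure, not assessed as caused | SAE; to sponsor and REC, form within 48 hours | Not reported to sponsor | Direct contradiction |
| Unrelated, and meeting the AE definition | Not an SAE; entered in the AE log, which goes to the sponsor every 3 months | Not reported to sponsor | No conflict with the SAE rule; conflict with the log route |
| Worsening of disease present at baseline | May fall outside the AE definition, and so outside the log | Not reported to sponsor unless assessed as caused | No assured route to the sponsor |

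Three further observations follow.

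1. **The ordering is inverted.** A non-fatal hospital admission partly due to the procedure must be reported within 48 hours. A sudden death with the same degree of relatedness need not be reported to the sponsor under 12d.

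2. **The causality anchor moves.** Section 12a refers to *the procedure*, 12b to *the treatment* and 12d to *study procedures*, and section 12 defines none of them. Section 10 is headed Study Procedures and includes the management review (10.5), which suggests that PGx-prompted prescribing counts. Section 9.3, however, describes consent as consent to a saliva sample, and sections 10.5 and 12 leave the prescribing decision to the physician, which invites a narrower reading. On that reading a death after a prescribing change would not be tested against the change at all.

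3. **The log is a partial backstop.** It is routinely sent only quarterly. The carve-out in 12a is loosely punctuated, but on its natural reading it removes worsening of baseline disease. In a population treated for long-term conditions, cardiovascular disease among them, that is a foreseeable cause of death.

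**The case against.** The strongest reply is that this is a wording conflict of limited reach. Much of that reply stands.

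- A clearly unrelated death is not an SAE under 12a, so leaving it out of SAE reporting does not breach the 12c rule. The conflict with that rule covers only deaths possibly or partly due to the procedure.
- A fatal event that meets the AE definition is still entered in the notes, the CRF and the AE log, and the log reaches the sponsor. A reader might infer that the sponsor could not detect a mortality signal. The documents do not support that: the log provides a route, though a slow and incomplete one. The study is also uncontrolled, and faster notification would not supply a comparator.
- A reader might also infer that deaths would be hidden from the 1-year outcomes and bias them. Section 12d governs notification, not the collection of outcome data. Follow-up draws on GP record review as well as questionnaires (section 10.2), and how deaths are handled in the 1-year measures is commonly left to a statistical analysis plan, which is not to hand.
- Section 12c defers to the sponsor's safety procedure for non-CTIMP studies. It is not shown and may settle some of this in practice.

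What does not stand is the suggestion that the log makes the conflict harmless. A quarterly log is not expedited reporting, 12a leaves some deaths outside it, and read literally the word *only* in 12d conflicts with the log route as well. An unseen procedure does not cure a protocol that gives sites two incompatible instructions.

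**Conclusion.** The contradiction is established from the protocol's own text and should be corrected. A site that follows 12d would not notify the sponsor of deaths possibly or partly related to the study, although 12a and 12c require it. The same section sets two timelines for deaths assessed as caused, and leaves open whether a PGx-prompted prescribing change falls within the causality assessment.

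The size can be described but not counted. A reader might apply an assumed annual death rate to the 500 participants. That would give all-cause deaths, most of which may lie outside the conflicting group, and it would rest on a rate the protocol does not supply. The conclusion needs no such figure. It rests on reading *caused by* as stricter than *wholly or partly due to*, and *only* as meaning what it says.

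**What to change.** 1. Delete the *only* restriction in 12d, and state that every death meeting the 12a SAE definition is reported to the sponsor and the REC.
2. Use one relatedness test and one term for the exposure throughout 12a to 12d, stating expressly that it covers PGx-informed prescribing changes as well as sampling.
3. Reconcile the immediate report in 12d with the 48-hour rule in 12c. The choice is the sponsor's, but it should be made openly: simply pointing 12d to the 12c timeline would silently drop the immediate report for deaths assessed as caused.
4. Record all other deaths, with date and cause, in the CRF and the AE log, including those from worsening of baseline disease.

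Expedited reporting of every death, whatever its cause, is not needed to remove the contradiction. The cost is a short redraft of section 12, submitted as an amendment, and a small amount of extra reporting. The practices already hold the participants' records, so recording date and cause should add little work.

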## 13 Data management and quality assurance

## a. Confidentiality

All data will be handled in accordance with the current Data Protection laws.

The samples and questionnaire will not bear the participant's name or other directly identifiable data. The participant's trial Identification Number (ID) only will be used foridentification. The primary care EHR can be used to cross reference participants' identifiable information.

#### b. Data collection tool

Questionnaire data will be collected in the OpenApp study registry. Patients will be offered support to complete the questionnaire by their practice.

